5.7.4 Summary of treatment outcome assignment

The below table provides treatment outcome assignments for both uncorrected and PCR-corrected ACPR at a given Day, say D where D can be 15, 29, or 43, for various specific scenarios.

Table 5-13 Derivation Criteria of uncorrected ACPR and PCR- corrected ACPR

Criteria	PP Analysis Set (PPS)		ITT Analysis Set	
	Treatment Outcome uncorrected ACPR	Treatment Outcome PCR-adjusted ACPR	Treatment Outcome uncorrected ACPR	Treatment Outcome PCR-adjusted ACPR
1. Completed up to Day (D) without re-emergence (new infection/ recrudescence) of parasites after initial clearance	Responder	Responder	Responder	Responder
2. Missing assessment on Day (D), but parasite free (No P. falciparum asexual parasites) after Day (D).	Responder	Responder	Responder	Responder
3. Missing assessment on Day (D), new infection (confirmed by PCR result) at first assessment after Day (D).	Non-responder	Responder	Non-responder	Responder
4. Early treatment failure from Day 2 to Day 4.	Non-responder	Non-responder	Non-responder	Non-responder
5. Late clinical failure from Day 5 to Day 7.	Non-responder	Non-responder	Non-responder	Non-responder
6. Receive non-study anti-malarial medication during the treatment period	Excluded from PPS	Excluded from PPS	Non-responder	Non-responder
7. Recrudescence before or on Day (D) (thus on or after Day 8 to [D])	Non-responder	Non-responder	Non-responder	Non-responder
8. New infection/PCR negative on Day (D).	Non-responder	Responder	Non-responder	Responder
9. New infection/PCR negative before Day (D) (thus on or after Day 8 to before (D))	If D <=29, excluded from PPS; If D=43, Non-responder	If D <= 29, excluded from PPS; if D=43, non-responder/	Non-responder	Non-responder/responder/KM-censoring

		responder/KM-censoring;		
10. Re-emergence before or on Day (D) but PCR result is indeterminate or missing.	Non-responder	Excluded from PPS if D ≤ 29 or non-responder/KM-censoring if D=43	Non-responder	Non-responder/KM-censoring
11. Missing assessment on Day (D), recrudescence (confirmed by PCR result) at first assessment after Day (D).	If D=29, excluded from PPS; if D=15, non-responder/KM-responder; NA for D=43	If D=29, excluded from PPS; if D=15, non-responder/ KM-responder; NA for D=43	Non-responder/ KM-responder	Non-responder/ KM-responder
12. Other Plasmodium species on Day (D) (in the absence of P. falciparum).	Responder	Responder	Responder	Responder
13. Other Plasmodium species before Day (D) (in the absence of P. falciparum).	If taking non-study drug prior to D29, excluded from PPS; otherwise, responder/ KM-censoring	If taking non-study drug prior to D29, excluded from PPS; otherwise, Responder/ KM-censoring	Responder/ KM-censoring	Responder/ KM-censoring
14. Other Plasmodium species before or on Day (D) (in the presence of P. falciparum), PCR-analysis result missing or indeterminate.	Handled as the Criteria 10, 12, and 13	Handled as Criteria 10, 12, and 13	Handled as Criteria 10, 12, and 13	Handled as Criteria 10, 12, and 13
15. Prematurely study discontinued from the study without parasite re-emergence before Day (D) and received SoC.	If discontinued before D29, excluded from PPS; if D=43,	If discontinued before D29, excluded from PPS; if D=43, non-	Non-responder/KM-censoring	Non-responder/KM-censoring

	Non-responder/KM-censoring	responder/KM-censoring		
16. Missing assessment on Day (D), no more assessments thereafter.	If D ≤ 29, excluded from PPS; Otherwise: non-responder/KM-censoring	If D ≤ 29, excluded from PPS; Otherwise: non-responder/KM-censoring)	Non-responder/KM-censoring	Non-responder / KM-censoring
17. Prematurely discontinued from the study before Day (D) and no record of SoC.	Same as Criterion 16	Same as Criterion 16	Same as Criterion 16	Same as Criterion 16

Note: '/' indicates separate analysis, e.g., 'non-response/KM-censoring' indicates one analysis considering outcome as non-responder and another analysis using KM method considering outcome as censored

NA: Not applicable; SoC: Standard of care

If a scenario meets multiple criteria, the worst case (non-responder) is used.

5.8 Rule of exclusion criteria of analysis sets

Table 5-14 Protocol deviations and non-PD criteria leading to exclusion from analysis sets

Analysis Set	PD (Description and ID) that causes Patients to be excluded	Non-PD criteria that cause Patients to be excluded
Randomized	
 Informed Consent for study participation or parental consent not obtained and patient entered trial (INCL05) 	
 Not randomized Misrandomized if identified from IRT
FAS	NA	
 Not in Randomized set Baseline parasitaemia count is 0 or missing No study drug taken
PPS	
 Parasite specie is other than Plasmodium falciparum OR mixed infection (INCL03) Baseline plasmodium falciparum parasite count <1000/uL or ≥150000/uL (INCL04) at the time of prescreening for the Run-in; plasmodium falciparum parasite count < 1,500 or ≥ 150,000 /uL parasites/μL at the time of pre-screening for Cohorts 1 and 2 No fever within the past 24 hours at baseline (INCL06) Prohibited non-antimalarial medications that may have effect on efficacy if received before the Day 29 visit without being falciparum treatment failures (COMD001A) Only for Run-in Cohort, do not fully comply with the food guidelines according to randomization (with OTH04 either day) 	
 Not in FAS; <80% of randomized study medication taken Received non-study concomitant antimalarial drugs during the treatment period Received non-study concomitant antimalarial drugs after the treatment period between Day 4 and Day 29 without experiencing treatment failure Not classified as non-responder before Day 8, no positive blood smear parasite on Day 8 onwards, and blood smear parasite result is missing at Day 29 and later (early discontinued) Not classified as non-responder before Day 8, have at least one positive blood smear parasite result between Day 8 and Day 29 which cannot be determined as recrudescent or new infection based on PCR genotyping and have parasites cleared prior to the positive blood smear parasite; Not classified as non-responder before Day 8, have a new infection prior to study Day 27 and have

		
parasites cleared prior to the positive blood smear parasite
 
 Not classified as non-responder before Day 8, no positive blood smear parasite before Day 29, blood smear parasite result is missing at Day 29, and blood smear parasite result is not negative or new infection at Day 43
SAF	NA	
 Not in Randomized set No study drug taken
PK	
 Patients who received concomitant prohibited medication which may have an impact on PK exposure 	
 Not in SAF No evaluable pharmacokinetic parameter data Compliance is <100% of randomized study medication taken

6 Reference

Stepniewska K and White NJ (2006) Some considerations in the design and interpretation of antimalarial drug trials in uncomplicated falciparum malaria. *Malaria Journal*; 5:127.

Collett, D. (1994), *Modeling Survival Data in Medical Research*, London: Chapman & Hall.

SAS/STAT ® 9.1 User's Guide. Cary, NC: SAS Institute Inc.

Brookmeyer, R. and Crowley, J. (1982) A confidence interval for the median survival time. *Biometrics*, 38, 29-41. doi:10.2307/2530286

Fourth Report on Diagnosis, Evaluation and Treatment of High Blood Pressure in Children and Adolescents. *Pediatrics* 2004; 114; 555 (see section 5.5.1 for detailed computation)

BMI-for-age percentiles categories (P3, P5, P10, P25, P50, P75, P85, P90, P95, P97) are obtained from the WHO Growth Charts (<http://www.who.int/childgrowth/en/>)

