Population	The study population will consist of male and female patients (Run-in Cohort: 12 to < 18 years old and ≥ 35.0 kg; Cohort 1: 2 to < 12 years old and ≥ 10.0 kg; Cohort 2: 6 months to < 2 years old, weight ≥ 5.0 kg) with confirmed uncomplicated P. falciparum malaria. In the Run-In Cohort, patients will have malaria symptoms and P. falciparum counts of ≥ 1,000 and ≤ 150,000 parasites/μL at pre-screening. In Cohort 1 and Cohort 2, patients will have malaria symptoms and P. falciparum counts of ≥ 1,500 and ≤ 150,000 parasites/μL at pre-screening.

Key Inclusion criteria	
 
• In Run-in Cohort: Male and female patients 12 to < 18 years of age, with a body weight <math>\geq 35.0</math> kg; In Cohort 1: Male and female patients 2 to < 12 years of age, with a body weight <math>\geq 10.0</math> kg; In Cohort 2: Male and female patients 6 months to < 2 years of age, with a body weight <math>\geq 5.0</math> kg
 
• Microscopic confirmation of P. falciparum by Giemsa-stained thick and thin films
 
• P. falciparum parasitemia of <math>\geq 1,000</math> and <math>\leq 150,000</math> parasites/<math>\mu</math>L at the time of pre-screening for Run-in Cohort
 
• P. falciparum parasitemia of <math>\geq 1,500</math> and <math>\leq 150,000</math> parasites/<math>\mu</math>L at the time of pre-screening for Cohorts 1 and 2
 
• Axillary temperature <math>\geq 37.5</math> °C or oral/tympanic/rectal temperature <math>\geq 38.0</math> °C; or history of fever during the previous 24 hours (at least documented verbally)
 
• Written informed consent has been obtained from parent / legal guardian before any assessment is performed. If the parent / legal guardian is unable to read and write, then a witnessed consent according to local ethical standards is permitted. Patients who are capable of providing assent, must provide assent with parental/legal guardian consent or as per local ethical guidelines
 
• The patient and his/her parent/legal guardian is able to understand and comply with protocol requirements, instructions and protocol-stated restrictions and is likely to complete the study as planned.
 

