#### **5.1 Inclusion criteria**

Patients eligible for inclusion in this study must meet **all** of the following criteria:

1. In Run-in Cohort: Male and female patients 12 to < 18 years of age, with a body weight  $\geq 35.0$  kg  
In Cohort 1: Male and female patients 2 to < 12 years of age, with a body weight  $\geq 10.0$  kg  
In Cohort 2: Male and female patients 6 months to < 2 years of age, with a body weight  $\geq 5.0$  kg
2. Microscopic confirmation of *P. falciparum* by Giemsa-stained thick and thin films

3. *P. falciparum* parasitemia of  $\geq 1,000$  and  $\leq 150,000$  parasites/ $\mu\text{L}$  at the time of pre-screening for the Run-in Cohort; and *P. falciparum* parasitemia of  $\geq 1,500$  and  $\leq 150,000$  parasites/ $\mu\text{L}$  at the time of pre-screening for Cohorts 1 and 2
4. Axillary temperature  $\geq 37.5$  °C or oral/tympanic/rectal temperature  $\geq 38.0$  °C; or history of fever during the previous 24 hours (at least documented verbally)
5. Written informed consent has been obtained from parent / legal guardian before any assessment is performed. If the parent/legal guardian is unable to read and write, then a witnessed consent according to local ethical standards is permitted. Patients who are capable of providing assent, must provide assent with parental/legal guardian consent or as per local ethical guidelines
6. The patient and his/her parent/legal guardian is able to understand and comply with protocol requirements, instructions and protocol-stated restrictions and is likely to complete the study as planned

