2.2 Analysis sets

Randomized set

All patients who are randomized into the study.

Full analysis set (FAS)

FAS will be comprised of all patients from Randomized set who take at least one dose of study treatment during the treatment period and whose baseline *P. Falciparum* asexual parasitaemia count is greater than 0. Following the intent-to-treat principle, patients will be analyzed according to the treatment group assigned to at randomization.

Unless otherwise specified, misrandomized patients will be excluded from the FAS.

Misrandomized patients, if identified from IRT, include patients who are screen-failures, but have been randomized by the investigator before eligibility was finally assessed or mistakenly, and have not been treated. If patients were re-screened and successfully randomized, they will be included in the randomized set according to the treatment assigned in the last randomization.

Safety set (SAF)

Safety set includes all patients who take at least one dose of study drug during the treatment period. Patients will be analyzed according to treatment received. In particular, patient will be analyzed in the same treatment group as randomized if s/he receives at least one dose of the study medication of that group. For the PK run-in cohort, all patients to receive the same dose in either fasted or fed condition.

Per-protocol set (PPS)

Per-protocol set will be comprised of patients in FAS who

- did not have any important protocol deviations affecting efficacy
- took at least 80% dosages of randomized study medication(s). If a patient vomited the original dose but did not vomit the replacement dose, the patient is considered as taking the dose of study medication. Since a partial compliance, such as 83%, etc., can be calculated based on the actual dosage taken (see [Section 2.4.1](#)), this allows patients to take partial dosages.
- did not take non-study medications with anti-malaria activity prior to Day 29 visit unless experiencing any treatment failure (ETF, LCF, LPF) (e.g new infections between Day 8 and Day 29), and PCR corrected ACPR status at Day 29 is defined, ie, at least one of the following criteria is met:
 - a. classified as treatment failure before Day 8 (see [Section 2.1.1](#))
 - b. had parasitaemia present on Day 8 or later without parasite clearance before (eg., parasite present Day 15 and parasite was not cleared before Day 15).
 - c. absent from parasitaemia at Day 29 or later,

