 - d. had a recrudescence if parasitaemia is present from Day 8 to Day 29, or
 - e. had a new infection at Day 29 visit or later

Food noncompliance in the Run-in cohort is considered as important PD. Important protocol deviations for exclusion from PPS are specified in [Table 5-14](#) and will be identified by the clinical team before the database lock.

PK analysis set

Run-in Cohort

PK Analysis set: All the subjects in the safety analysis set who have at least one evaluable PK concentration. A profile is considered evaluable for that period if following conditions are satisfied:

- Participants took at least 80% dosages of randomized study medication
- If a patient vomited the original dose but did not vomit the replacement dose
- Participants with no protocol deviations (PD) that may have an impact on the PK data

PK analysis set-partial food compliance: all subjects in the PK analysis set who are compliant to meal criteria (within 30 minutes of drug administration and took at least 70% of the standard meal) on any of the two dosing days.

PK analysis set-Full food compliance: all subjects in the PK analysis set who are compliant to meal criteria (within 30 minutes of drug administration and took at least 70% of the standard meal) on both dosing days.

Note that meal non-compliance for the run-in cohorts is identified using the PD (protocol deviation) code OTH04.

Cohort 1 and Cohort 2

PK Analysis set: All the subjects in the safety analysis set who have at least one evaluable PK concentration. A profile is considered evaluable for that period if following conditions are satisfied:

- Participants took at least 80% dosages of randomized study medication
- If a patient vomited the original dose but did not vomit the replacement dose
- Participants with no protocol deviations (PD) that may have an impact on the PK data

PK analysis set-partial food compliance*: all subjects in the PK analysis set who are compliant to meal criteria (within 1 hour (± 5 min) of drug administration and took at least 70% of light meal) on both Days 2 and 3.

PK analysis set-Full food compliance*: All subjects in the PK analysis set who are compliant to meal criteria (within 1 hour (± 5 min) of drug administration and took at least 70% of light meal) on all three dosing days.

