2.5.2 Statistical hypothesis, model, and method of analysis

The statistical null hypothesis is that the difference in PCR-corrected ACPR rate at Day 29 between KAF156 and LUM-SDF combination and Coartem[®] is at most -10% with the alternative hypothesis that it is greater than -10%. The statistical hypothesis will be evaluated using the lower limit of two-sided 95% confidence interval (CI) for the difference between two treatment groups.

If Cohort 2 does not stop early, two-sided 95% CI for the difference between two treatment groups will be provided for Cohorts 1 and 2 pooled using Mantel-Haenszel estimate of the common risk difference stratified by cohort (see [SAS manual version 13.2 Pages 2681-2682, 2014](#)). If the lower limit of 2-sided 95% CI for the difference is greater than -10%, the null hypothesis will be rejected.

In case that Cohort 2 stops early, such as after the first 24 patients, two-sided 95% CI for the difference between two treatment groups will be provided for Cohort 1 alone using the Wilson

uncorrected method. If the lower limit of 2-sided 95% CI for the difference is greater than -10%, the null hypothesis will be rejected.

The statistical hypothesis testing will be evaluated based on the PPS.

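### SAP Table 5-14 lists a pre-screening count of exactly 150,000/uL as a PPS-excluding deviation, although protocol inclusion criterion 3 admits it

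*SAP*

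**What the plan says.** The protocol states the entry range in its summary, Section 3, Section 5, inclusion criterion 3 in Section 5.1, and Section 8.1. For Cohorts 1 and 2 the summary requires "counts of ≥ 1,500 and ≤ 150,000 parasites/μL at pre-screening". The Run-in Cohort has a lower limit of 1,000/uL and the same inclusive upper limit.

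SAP Table 5-14 lists the deviations that remove a patient from the PPS. For Cohorts 1 and 2 it gives a pre-screening "parasite count < 1,500 or ≥ 150,000 /uL". For the Run-in Cohort it gives "<1000/uL or ≥150000/uL (INCL04"), also tied to pre-screening.

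Three further statements give the table its force:

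- SAP Section 2.2: "Important protocol deviations for exclusion from PPS are specified in" Table 5-14. The clinical team identifies them before database lock.
- SAP Section 2.5.2: "The statistical hypothesis testing will be evaluated based on the PPS".
- SAP Section 4 declares no change to the protocol-specified analyses.

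For the FAS, SAP Section 2.2 asks only that the baseline "asexual parasitaemia count is greater than 0". It sets no upper limit.

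**The concern.** A PPS exclusion based on an eligibility deviation should be the exact complement of the eligibility criterion. The lower limits meet that test: 1,500/uL and above is eligible, and below 1,500/uL is a deviation. The upper limits do not, because 150,000/uL is both eligible and a listed deviation. Nothing in either document suggests that a stricter limit was intended, so this looks like a drafting slip.

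It deserves correction because the table decides who is in the primary test. A child at the boundary would be in or out of that test according to which document the deviation check was written from. That should be settled by the rule before the data are seen.

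**Working it through.** **1. The ranges side by side (Cohorts 1 and 2, count at pre-screening)**

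| Count (/uL) | Protocol criterion 3 | SAP Table 5-14 | Agree? |
|---|---|---|---|
| below 1,500 | not eligible | excluded from PPS | yes |
| 1,500 to below 150,000 | eligible | retained | yes |
| exactly 150,000 | eligible | excluded from PPS | no |
| above 150,000 | not eligible | excluded from PPS | yes |

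The conflict is confined to one value. The Run-in clause has the same conflict, but that cohort is analyzed separately (Protocol Section 12) and does not enter the primary test.

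**2. How a count of exactly 150,000 could arise**

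Protocol Section 8.3.1 gives density = parasites × actual WBC / WBC counted. With 200 leukocytes counted, exactly 150,000 requires parasites × WBC = 150,000 × 200 = 30,000,000. For example, 3,000 parasites at an assumed WBC of 10,000/uL gives 3,000 × 10,000 / 200 = 150,000. This is possible but needs an exact coincidence or rounding. I assume 0 of about 220 children as the likely number.

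**3. The plan's own power figure**

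Inputs from SAP Section 3.1.1: response 95% in both groups, margin 10 points, 1-sided alpha 2.5%, 92 evaluable per group, about 16% excluded from the PPS, about 220 randomized 1:1.

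- SE = √(2 × 0.95 × 0.05 / 92) = 0.0321.
- Power = Φ(0.10 / 0.0321 − 1.96) = Φ(1.15) = 87.5%. The stated figure is at least 87%, so it reproduces.
- Sample size: 92 / 0.84 = 109.5, rounded up to 110 per group, 220 in total. This also reproduces.

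Neither figure uses the 150,000 limit. If boundary exclusions did cost patients, the same formula gives 87.2% with 91 per group (two children lost) and 86.8% with 90 per group (four lost).

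**4. Effect of one excluded child on an arm's ACPR rate**

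Take 87 responders of 92, the whole number nearest to 95% (0.95 × 92 = 87.4).

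- No exclusion: 87/92 = 94.57%.
- One responder excluded: 86/91 = 94.51%, a fall of 0.06 points.
- One failure excluded: 87/91 = 95.60%, a rise of 1.03 points.

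At the assumed 95% response rate the excluded child would be a responder about 19 times in 20. The larger shift needs both the exact count and a treatment failure.

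**The case against.** The best reply is that the child might never be dropped. The limit appears in a column of protocol deviations, the clinical team identifies those deviations, and a child at 150,000/uL has not deviated from criterion 3. SAP Section 2.1 also ties the analysis to Section 12 of the protocol, and SAP Section 4 declares no change. A team working from the protocol would keep the child; a programmed check copied from Table 5-14 would not. This part of the reply stands. A reader might infer that an eligible child is certain to be removed, but the documents support only that the table, applied as written, would do so.

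Other safeguards also stand. The count is taken before randomization and the rule is identical in both arms. SAP Section 2.5.4 repeats the primary analysis on the FAS, which keeps such a child. The design already allows for 220 − 184 = 36 children outside the PPS, and SAP Section 3.1.1 provides for extra randomization if the PPS falls short.

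A reader might also infer that round values near the limit are common, because Protocol Section 8.3.1 mentions thin-film counts per 1,000 red cells. The documents do not support this. No conversion to parasites/uL is given, thin films are read only when species identification is needed, and Table 8-5 makes red cell counts conditional on marked anaemia or a haemoglobin drop, and optional by site.

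None of this removes the contradiction. Table 5-14 is the list that SAP Section 2.2 names for PPS exclusions, and the FAS analysis is a sensitivity analysis, not the primary test.

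**Conclusion.** The contradiction is exact and lies in an operative rule for the primary analysis set, so Table 5-14 is wrong as written. It is a consistency point of minor weight. It concerns only Cohort 1 or 2 children recorded at exactly 150,000/uL, probably none of about 220. That number is an assumption, because the documents give no distribution of counts. One such child would most likely move an arm's rate by less than 0.1 point, and by about 1.0 point if that child were a failure, against a margin of 10 points.

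A reader might go further and infer that the non-inferiority conclusion is biased or the trial underpowered. Neither follows. The rule cannot systematically favour an arm, the FAS analysis is untouched, and the planned power of at least 87% was calculated without reference to this limit.

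**What to change.** In SAP Table 5-14, PPS row, change the upper limit in both INCL04 clauses from 'at or above' to 'above' 150,000/uL, and make the same change in the matching deviation check. The exclusions then read: Run-in Cohort, below 1,000 or above 150,000/uL; Cohorts 1 and 2, below 1,500 or above 150,000/uL. INCL04 becomes the exact complement of inclusion criterion 3. Only the second clause bears on the primary test; the first is for consistency.

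In the same edit, drop the word baseline from the Run-in clause, since the clause concerns the pre-screening count and Protocol Section 3 takes the Day 1 pre-dose count as baseline.

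The cost is two inequality signs and one word, with no effect on sample size, data collection or conduct. The change should be made before database lock. If lock has already passed, confirm and document whether any patient left the PPS solely because of a count of exactly 150,000/uL.

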### 12.1 Analysis sets

The Randomized Analysis Set (RAS) consists of all randomized patients.

The Full Analysis Set (FAS) comprises all patients to whom study treatment has been assigned by randomization and who are treated with at least one dose of study drug with baseline *P. falciparum* asexual parasite count >0. According to the intent to treat principle, patients will be analyzed according to the treatment they have been assigned to during the randomization procedure.

The Safety Set includes all patients who received at least one dose of study treatment. Patients will be analyzed according to the study treatment received, where treatment received is defined as the randomized treatment if the patient took at least one dose of that treatment or the first treatment received if the randomized treatment was never received.

The Per-Protocol Set (PPS) is a subset of patients of the Full Analysis Set and is characterized by the following criteria:

- did not have important protocol deviations affecting efficacy,
- took at least 80% of study medication,
- did not take non-study drug antimalarial medications prior to Day 29 unless experiencing a treatment failure (ETF, LCF, LPF), and
- PCR corrected ACPR status at Day 29 can be defined

Important protocol deviations for exclusion from the PPS will be identified by the clinical team before database lock.

The PK set is a subset of the Full Analysis Set who had evaluable PK parameter/concentration data and took at least 80% of study medication.

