2.5.4 Sensitivity analyses

- The primary efficacy analysis will be repeated on the FAS using the statistical methods specified in [Section 2.5.2](#). Primary efficacy variable will be handled additionally for those patients who are excluded from the PPS as follows:
 - Presence of parasitaemia which cannot be determined to be recrudescence or new infection due to missing PCR data will be counted as non-responders (from the day of test)
 - Missing/undetermined responses at Day 29 due to missing blood smear data at the visit will be counted as non-responders unless there is a later blood smear test indicating no parasitemia.
 - Patients with new infection before Day 29 will be considered 1) not achieving PCR-corrected ACPR at Day 29 in one analysis and 2) and achieving PCR-corrected ACPR at Day 29 in another analysis
 - Patients who received non-study related anti-malarial medication without having reappearance of the parasites will be considered in the analysis as if they had not taken these drugs. This is because such cases will be very unlikely as administration of such medicines are expected only in case of the reappearance of the parasites. Note- Patients who take non-study anti-malarial medication due to repeated vomiting of study medication should be considered as treatment failure.

Note: These patients did not experience any treatment failure (ETF, LCF, or LPF). In case that non-PPS patients who experienced treatment failure, they will be included as non-responders if they received rescue medication for the treatment of *P. falciparum* malaria due to recrudescence or as responder for PCR corrected ACPR if they received rescue medication to treat a new infection on Day 29 visit.

- Patients who received non anti-malaria medication with potential anti-malarial activity without having reappearance of the parasites will be considered in the analysis as if they had not taken these drugs. This is because such medications will have minimal effect on efficacy.

- Although the objective of Run-in cohort is to investigate the food effect on bioavailability of KAF156 and lumefantrine, analyses related to primary and other secondary variables will be performed in Run-in cohort by treatment group, unless otherwise specified.

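### The COMD001A exclusion in SAP Table 5-14 does not require the treatment failure to come before the prohibited drug, so read literally, membership of the primary analysis set depends on the outcome

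*SAP*

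**What the plan says.** The formal test rests on one set: "The statistical hypothesis testing will be evaluated based on the PPS" (SAP 2.5.2; Protocol 12.4.2 agrees). Four places bear on who belongs to it.

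- Protocol 12.1 requires that the child "did not have important protocol deviations affecting efficacy", and SAP 2.2 that the child "did not have any important protocol deviations affecting efficacy". Neither attaches a condition on outcome. SAP 2.2 adds that the important deviations leading to exclusion are those listed in Table 5-14.
- Protocol 12.1 gives a failure exemption for antimalarials: the child "did not take non-study drug antimalarial medications prior to Day 29 unless experiencing a treatment failure (ETF, LCF, LPF), and" has a definable Day 29 status. SAP 2.2 gives it for a wider class: "did not take non-study medications with anti-malaria activity prior to Day 29 visit unless experiencing any treatment failure (ETF, LCF, LPF").
- SAP 5.8, Table 5-14, PPS row, lists as a deviation leading to exclusion: "Prohibited non-antimalarial medications that may have effect on efficacy if received before the Day 29 visit without being falciparum treatment failures (COMD001A"). A separate criterion covers non-study antimalarials taken "after the treatment period between Day 4 and Day 29 without experiencing treatment failure".
- SAP 2.5.4 repeats the primary analysis on the FAS. There, "Patients who received non anti-malaria medication with potential anti-malarial activity without having reappearance of the parasites will be considered in the analysis as if" the drug had not been taken.

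**The concern.** A failure exemption is sound when the drug follows the failure, because the outcome is already fixed. The COMD001A wording ties the exemption to being a failure and not to which came first. Take two children given the same prohibited drug on Day 6. One stays parasite-free and is excluded. The other recrudesces on Day 20 and is kept as a non-responder. Among users, successes are dropped and failures retained.

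The prohibited list includes CYP3A inducers such as rifampin and phenobarbital (Protocol 6.2.2; SAP Table 5-9). If such a drug lowers exposure, the retained failure may result from the very deviation that a per-protocol analysis is meant to remove.

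The stake is the set used for the non-inferiority decision. Treatment is open at the sites (Protocol 6.4), so co-medication could differ by arm. The arm with more use would look worse. More use on Coartem would favour non-inferiority, so the rule is not reliably conservative.

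**Working it through.** **1. The plan's own figure.** Inputs from SAP 3.1.1: 95% response in both arms, margin 10 points, one-sided 2.5%, 92 evaluable per arm. The standard error is √(2 × 0.95 × 0.05 / 92) = 0.0321. Power = Φ(0.10/0.0321 − 1.96) = 87.5%, which matches the stated 87% or more. With 16% excluded, 220 × 0.84 / 2 = 92.4 per arm, which also matches.

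**2. The three rates.** In one arm, let N non-users include c cured and M users include k cured. Suppose every user took the drug before any failure.

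- Exclude all users: c / N
- Keep all users: (c + k) / (N + M)
- Table 5-14 read literally: c / (N + M − k)

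The third is below the first when at least one user fails, and below the second when at least one user is cured. Enumeration of 45,045 integer cases with both a cured and a failing user found no exception apart from the trivial c = 0. Example: 79 of 83 non-users and 9 of 10 users cured gives 95.2%, 94.6% and 79/84 = 94.0%.

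**3. Size within an arm.** Let u be the share of users and t their cure rate, with non-users at 95%. The literal rate is 0.95(1 − u) / [(1 − u) + u(1 − t)]. Both u and t are assumptions; the documents give neither.

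| Users | Cure in users | Exclude all | Keep all | As written |
|---|---|---|---|---|
| 5% | 95% | 95.0% | 95.0% | 94.75% |
| 10% | 95% | 95.0% | 95.0% | 0.855/0.905 = 94.5% |
| 10% | 80% | 95.0% | 93.5% | 0.855/0.920 = 92.9% |
| 20% | 95% | 95.0% | 95.0% | 93.8% |
| 20% | 80% | 95.0% | 92.0% | 90.5% |

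**4. Size between arms, with no true difference.**

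- Equal use and equal user cure: expected difference 0. Holding 92 per arm, power falls from 87.5% to 84.3% at 10% users with 95% cure.
- 2% versus 10% use, user cure 95%: 0.931/0.981 − 0.855/0.905 = 94.90% − 94.48%, or 0.43 points before rounding.
- Same use, user cure 99%: about 0.09 points.
- Same use, user cure 80%: 0.931/0.984 − 0.855/0.920 = 94.61% − 92.93% = 1.68 points.

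For scale, the planned 95% interval has a half-width of 1.96 × 0.0321 = 6.3 points.

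**5. Where the ordering breaks down.** If no user fails, the literal rule equals exclude-all. With 11 users in an arm (10% of 110) at 95% cure, that has probability 0.95^11 = 0.57. Also, some retained users may be responders: a new infection in the Day 29 window can be a late parasitological failure yet a PCR-corrected responder (SAP Table 5-13, criterion 8). With r such users and f true failures, the rate becomes (c + r)/(N + f + r). With c/N at 95%, that is below exclude-all only if r/(r + f) < 0.95, that is, r < 19f. It remains below keep-all as long as some cured users are dropped.

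**The case against.** The best defence is that the COMD001A phrase can describe the child's status when the drug was taken. On that reading the Day 6 user is excluded whatever happens on Day 20, only children who had already failed are kept, and the rule is legitimate. The wording allows this reading but does not state it, so the ambiguity stands.

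Three stronger inferences are tempting, and the documents do not support them.

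- *That Table 5-14 invents an exemption in conflict with the PPS definition.* SAP 2.2 already extends the exemption from antimalarials to medications with anti-malaria activity, and it delegates the list of important deviations to Table 5-14. COMD001A can be read as carrying that out.
- *That the antimalarial criterion has the same gap.* SAP 2.4.2 classes an antimalarial as rescue only if used after study drug is stopped for failure. SAP 2.7.2.1 excludes non-rescue users before Day 29 from the PPS without regard to later outcome. Together these largely settle the order; only the Table 5-14 wording lags.
- *That the PPS rate always falls below both alternatives, or that the bias is 1.7 points.* The first fails when no user fails. The second needs an assumed fivefold imbalance in use and an assumed 80% cure in users. For drugs with potential antimalarial activity, lower cure is the less plausible direction, and SAP 2.5.4 expects their effect to be minimal.

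The plan also limits exposure to the problem. Protocol 6.2.2 bars new medication until the Day 7 evaluations are complete, except to treat adverse events. Deviations are identified before database lock, and the trial team is blinded in Cohorts 1 and 2. The FAS analysis keeps these children. It is a partial check only, since the FAS also differs from the PPS in its handling of missing data and new infections. I find no planned analysis that excludes all users.

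**Conclusion.** COMD001A leaves the order of drug and failure unstated. Taken literally, it makes membership of the primary analysis set depend on the outcome. The resulting PPS cure rate is below both consistent alternatives when users include at least one cure and one true failure, with few retained users counted as responders. Bias in the treatment difference also requires use, or cure among users, to differ by arm. Without any figure for use, a plausible size is a few tenths of a point: 0.4 points under the assumed 2% versus 10% use with 95% cure. It grows only if the drug lowers cure or use is common. This is unlikely by itself to decide the trial against a 10-point margin, but it is an avoidable ambiguity in the set on which the claim rests.

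**What to change.** Reword COMD001A so that timing decides: *exclude if first intake of a prohibited non-antimalarial medication that may affect efficacy is before the Day 29 assessment and before the first day of any treatment failure, whatever the later outcome; do not exclude if first intake is on or after the day of failure.* Keep the FAS analysis as the keep-all check. For the antimalarial criterion, only align the Table 5-14 wording with the rescue and non-rescue definitions in SAP 2.4.2 and 2.7.2.1.

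The cost is one SAP sentence and one date comparison, settled before database lock. A few failures that followed a prohibited drug leave the PPS; they remain failures in the FAS. The new rule is not fully independent of outcome, because a child who fails early has less time in which to be excluded, but it removes the selection among children who took the drug first.
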